3.4 TERTIARY/EXPLORATORY ENDPOINT(S) ANALYSIS

Not applicable.

3.5 MULTIPLICITY ISSUES

[figure not shown]
Multiplicity adjustment: to control overall Type I error at 0.05 level (2-sided), a gate-keeping procedure will be used. Two families of hypothesis testing will be established: family 1 of primary and family 2 of key secondary hypotheses. For the primary endpoint (change from baseline to Week 24 in HbA1c), no multiplicity adjustment is needed to control the Type I error since only one comparison of iGlarLixi versus IDegAsp will be performed.

If the primary endpoint is statistically significant at the 2-sided 0.05 level, a hierarchical testing procedure will be performed to test the following key secondary efficacy endpoints in the order specified in [Figure 1](#).

- Superiority in 2a and 2b will be tested at the 2-sided 0.025 level each.
- Only if 2a is statistically significant, 2c will be tested at the 2-sided 0.025 level.
- 2d will be tested at the 2-sided 0.05 level if both 2b and 2c are statistically significant, or at the 2-sided 0.025 level if only one of them is statistically significant.
- If 2d is statistically significant, 2e will be tested at the 2-sided 0.025 or 0.05 level based on the significant level passed from 2d.

This gate-keeping procedure will only apply for the primary analysis of the primary estimand for each endpoint. For other secondary hypotheses, no multiplicity adjustment will be applied.

Figure 1 - Graphical illustration of the gate-keeping procedure

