6.4 MEASURES TO MINIMIZE BIAS: RANDOMIZATION AND BLINDING

- The randomized intervention kit number list is generated centrally by Sanofi.
- The IMPs are packaged in accordance with this list.
- An interactive response technology (IRT) will generate the participant randomization list and allocates the intervention number and the corresponding intervention kits to the participants according to it.
- All participants will be centrally assigned to randomized study intervention using an IRT. Before the study is initiated, the telephone number and call-in directions for the IVRS and/or the log in information and directions for the IWRS will be provided to each site.
- Study intervention will be dispensed at the study visits summarized in the SoA.
- Returned study intervention should not be re-dispensed to the participants.
- The randomization will be stratified by value of screening HbA1c (<8%, ≥8%), and by use at screening of metformin alone or metformin +SGLT2 (Yes/No).
- The overall objective of this last stratification group is to ensure that participants who will need to discontinue their second OAD are well balanced between groups. Definition of a randomized participant: a participant from screened population who has been allocated to a randomized intervention regardless of whether the intervention was received or not.
- A participant cannot be randomized more than once in the study.
- This is an open-label study because of the existing differences in the type and features of pens used to administer the iGlarLixi and IDegAsp. To compensate for the lack of blinding, the Investigator and the Sponsor will not have access to the data of the primary efficacy parameters (HbA1c, objectively collected and measured at a central laboratory) obtained after baseline visit until the end of the study.
However, the study team may review the data for the primary efficacy parameter in descriptive statistics with the name of the IMP treatment masked during data review meetings.

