9.3.4 Multiplicity adjustment

[figure not shown]
Multiplicity adjustment: to control overall Type I error at 0.05 level (2-sided), a gate-keeping procedure will be used. Two families of hypothesis testing will be established: family 1 of primary and family 2 of key secondary hypotheses. For the primary endpoint (change from baseline to Week 24 in HbA1c), no multiplicity adjustment is needed to control the Type I error since only one comparison of iGlarLixi versus IDegAsp will be performed.

If the primary endpoint is statistically significant at the 2-sided 0.05 level, a hierarchical testing procedure will be performed to test the following key secondary efficacy endpoints in the order specified in [Figure 2](#).

- Superiority in 2a and 2b will be test at the 2-sided 0.025 level each.
- Only if 2a is statistically significant, 2c will be tested at the 2-sided 0.025 level.
- 2d will be tested at the 2-sided 0.05 level if both 2b and 2c are statistically significant, or at the 2-sided 0.025 level if only one of them is statistically significant.
- If 2d is statistically significant, 2e will be tested at the 2-sided 0.025 or 0.05 level based on the significant level passed from 2d.

This gate-keeping procedure will only apply for the primary analysis of the primary estimand for each endpoint. For other secondary hypotheses, no multiplicity adjustment will be applied.

Figure 2 - Graphical illustration of the gate-keeping procedure

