3.3.1 Key secondary efficacy endpoints

3.3.1.1 *Definition of endpoints*

The key secondary efficacy endpoints are:

- 2a The absolute change from baseline to week 24 in HbA1c.
- 2b The absolute change from baseline to week 24 in body weight.
- 2c Proportion of participants reaching HbA1c<7% at week 24.
- 2d Proportion of participants reaching HbA1c targets <7% without body weight gain at Week 24.
- 2e Proportion of participants reaching HbA1c <7% with no body weight gain at Week 24 and no hypoglycemia (defined as ADA level 1, 2 or 3) during treatment.

3.3.1.2 *Main analytical approach*

Key secondary efficacy endpoint 2a

If the primary objective is met, the key secondary efficacy endpoint 2a will be analyzed with the primary estimand defined the same as the primary estimand of the primary endpoint, except that 2-sided 97.5% CI and superiority p-value from ANCOVA will be provided if endpoint is to be tested as per the gate-keeping procedure defined in [Section 3.5](#); otherwise, 95% CI will be provided and no p-value will be provided.

Key secondary efficacy endpoint 2b

The key secondary efficacy endpoint 2b will be analyzed with the primary estimand defined according to the following attributes

- Endpoint: Change in body weight from baseline to Week 24.
- Treatment condition: iGlarLixi will be compared to IDegAsp.
- Analysis population: All randomized participants
- Intercurrent events (IE):
 - Treatment discontinuation IE will be handled with the treatment policy strategy: the endpoint will be assessed based on all assessments irrespective of the treatment discontinuation
 - The initiation of rescue medication IE will be handled with the treatment policy strategy: the endpoint will be assessed based on all assessments irrespective of the treatment discontinuation
- Population-level summary: LS Means difference between treatments from ANCOVA with treatment group, randomization stratum of HbA1c and previous OAD and baseline body weight as covariates. SE, 2-sided 97.5% CI and superiority p-value from ANCOVA will be provided if endpoint is to be tested as per the gate-keeping procedure defined in

[Section 3.5](#); otherwise, 95% CI will be provided and no p-value will be provided. Missing data will be imputed by multiple imputations using missingness patterns based on treatment completion, and under the missing at random (MAR) assumption within each pattern. The same imputation method as of the primary estimand of the primary endpoint will be used.

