Descriptive statistics for body weight and changes from baseline will be provided for baseline and each visit by treatment group. Mean changes from baseline with the corresponding standard error will be plotted over time.

Key secondary efficacy endpoint 2c, 2d, and 2e

The key secondary efficacy endpoints 2c, 2d, and 2e will be analyzed with the primary estimand defined according to the following attributes:

- Treatment condition: iGlarLixi will be compared to IDegAsp.
- Analysis population: All randomized participants
- Intercurrent events (IE):
 - Treatment discontinuation IE will be handled with the treatment policy strategy: the endpoint will be assessed based on all assessments irrespective of the treatment discontinuation
 - The initiation of rescue medication IE will be handled with the treatment policy strategy: the endpoint will be assessed based on all assessments irrespective of the initiation of rescue medication
- Population-level summary: Odds ratio between treatments from logistic regression model adjusting for treatment group, randomization stratum of previous OADs, and appropriate baseline covariates. The proportion of participants in each treatment group will be provided, as well as the odds ratio between groups (HbA1c and body weight will be included as baseline continuous covariates when considered in the definition of endpoints). If an endpoint is to be tested as per the gate-keeping procedure defined in [Section 3.5](#), 2-sided CI at the specified significance level and the associated p-value will be provided; otherwise, 95% CI will be provided and no p-value will be provided. For the categorical secondary endpoints in which HbA1c is assessed at Week 24, all values at Week 24 will be used to determine whether a participant is a responder or not, even if they are measured after IMP discontinuation or introduction of rescue therapy. If no assessment is available at Week 24, participants will be treated as non-responders.

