3.3.1.3 Supplementary analysis

Secondary estimands of key secondary efficacy endpoints 2a and 2b

Under hypothetical strategy, measurements after treatment discontinuation and/or initiation of rescue medication will be considered as missing data.

A MMRM, under the missing at random framework, will be performed for the secondary estimands of both key secondary efficacy endpoints 2a and 2b. The model will include treatment, randomization stratum of HbA1c, randomization stratum of previous OADs, visit, treatment-by-visit interaction as fixed effects, appropriate baseline value and baseline-by-visit interaction as continuous covariate. For the analysis of HbA1c, the randomization stratum of HbA1c will be removed from the MMRM model given that the baseline HbA1c continuous value is already in the model. The MMRM model will be implemented using SAS® (Version 9.4 or higher) MIXED procedure (PROC MIXED) with an unstructured correlation matrix to model the within-participant errors. Parameters will be estimated using the restricted maximum likelihood method with the Newton-Raphson algorithm. Denominator degree of freedom will be estimated using the Kenward-Roger approximation by fitting values from post-randomization scheduled visits. LS Means difference between treatments, SE, 2-sided 97.5% CI, and 2-sided superiority p-value from MMRM will be provided if endpoint is to be tested as per the gate-keeping procedure defined in [Section 3.5](#); otherwise, 95% CI will be provided and no p-value will be provided.

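### Optional improvement: the gate-keeping rules control family-wise error at 0.05 but pass no alpha on after 2e, so 2a, 2b and 2c are never tested above 0.025

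*SAP*

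**What the plan says.** SAP 3.5 and Protocol 9.3.4 give the same rules. Once non-inferiority on the primary endpoint is shown at 2-sided 0.05, the key secondary family opens. SAP 3.5 states: "Superiority in 2a and 2b will be tested at the 2-sided 0.025 level each"; the protocol has the same sentence: "Superiority in 2a and 2b will be test at the 2-sided 0.025 level each". 2c is tested at 0.025 only after 2a succeeds. 2d is tested at 0.05 if both 2b and 2c succeed, and at 0.025 if only one does. The last rule is: "If 2d is statistically significant, 2e will be tested at the 2-sided 0.025 or 0.05 level based on the significant level passed from 2d". No rule follows it. The figure that illustrates the procedure is not reproduced in the text available for either document.

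The interval rules fit fixed levels for 2a and 2b. For 2a, SAP 3.3.1.2 plans: "2-sided 97.5% CI and superiority p-value from ANCOVA will be provided if endpoint is to be tested as per the gate-keeping procedure". It uses the same 97.5% level for 2b, and SAP 3.3.1.3 does so for the secondary estimand of both: "2-sided 97.5% CI, and 2-sided superiority p-value from MMRM will be provided if endpoint is to be tested". For 2c, 2d and 2e, SAP 3.3.1.2 instead lets the interval follow the test level: "2-sided CI at the specified significance level and the associated p-value will be provided".

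**The concern.** Alpha that reaches 2e and is used successfully there is not returned to endpoints that are still open. Suppose 2b, 2d and 2e are rejected and 2a gives p = 0.03. As written, HbA1c superiority is not claimed and 2c is not tested, although a procedure with the same stated 0.05 limit could test 2a at 0.05 at that point.

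Such a pattern is plausible. Protocol 2.2 links premix insulin to weight gain and describes iGlarLixi as weight neutral, so 2b may well succeed. The sample size assumes a true HbA1c difference of zero, so the trial was not sized for 2a. At stake is a key secondary superiority claim in a narrow set of outcomes. The primary non-inferiority test is not touched.

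**Working it through.** **1. Inputs.** From SAP 3.5: starting levels of 0.025 on 2a and 0.025 on 2b; alpha flows 2a to 2c, 2c to 2d, 2b to 2d and 2d to 2e; nothing leaves 2e. From SAP 4: 290 per arm, SD 1.05%, dropout 10%, margin 0.3%, true difference zero.

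**2. Reproducing the plan's own figures.** Five hypotheses give 2^5 - 1 = 31 possible sets of true nulls. For each set, reject everything outside it and add up the alpha left inside it. The largest total is 0.05, so the stated family-wise level is confirmed under any dependence. Simulation of the text rule (200,000 draws per setting) gave at most 0.0507, which is 0.05 within simulation error. The sample size also reproduces: 258 (normal) or 259 (t-test) evaluable per arm, and divided by 0.9 this is 287 or 288, against 290 planned.

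**3. Where alpha is left over.** The 24 sets that contain 2d or 2e all keep 0.05. The seven sets without them are:

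| True nulls | Alpha held, current text | With return from 2e |
|---|---|---|
| 2a | 0.025 | 0.05 |
| 2b | 0.025 | 0.05 |
| 2c | 0.025 | 0.05 |
| 2a, 2c | 0.025 | 0.05 |
| 2a, 2b | 0.05 | 0.05 |
| 2b, 2c | 0.05 | 0.05 |
| 2a, 2b, 2c | 0.05 | 0.05 |

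So 24 + 3 = 27 sets use 0.05 and four use 0.025. For {2a}, for example, the 0.025 that started on 2b moves to 2d, then to 2e, and is then lost.

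**4. The return rule.** Add edges from 2e to 2a and from 2e to 2b, weight 1/2 each, with the standard graph update. All 31 sets then use 0.05 and none exceeds it. On 300,000 random p-value vectors, the current rules and the wording proposed under the fix each matched their closed test with no discrepancy. The proposed wording lost no rejection and added at least one in 9,710 vectors.

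**5. Which outcomes change.** Evaluable per arm: 290 x 0.9 = 261. SE = 1.05 x sqrt(2/261) = 0.0919. The threshold for 2a is 2.241 x 0.0919 = 0.206% at level 0.025 and 1.960 x 0.0919 = 0.180% at 0.05. 2a therefore changes only if the observed difference falls between about 0.180% and 0.206% and 2b, 2d and 2e are all rejected. 2c changes when 2a, 2b, 2d and 2e are rejected and its own p-value lies between 0.025 and 0.05. It also changes at any p up to 0.05 when 2a passes only on retest, because it was not testable before. 2b changes when 2a, 2c, 2d and 2e are rejected and its p-value lies between 0.025 and 0.05.

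**6. Ceiling on the gain for 2a** (261 per arm, SD 1.05%; the differences are assumptions):

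| True difference | Power at 0.025 | Power at 0.05 | Ceiling (points, before rounding) |
|---|---|---|---|
| 0.10% | 12.4% | 19.2% | 6.7 |
| 0.15% | 27.1% | 37.2% | 10.0 |
| 0.20% | 47.4% | 58.6% | 11.2 |
| 0.25% | 68.4% | 77.6% | 9.3 |
| 0.30% | 84.7% | 90.4% | 5.7 |

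These are upper limits, because 2b, 2d and 2e must succeed first.

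**7. Gain at a true difference of 0.20%** (20,000 simulated trials per setting). Assumed, not in the documents: control HbA1c 7.0% at Week 24, weight SD 3 kg, control weight gain 1 kg, HbA1c-weight correlation 0.1, and the weight and hypoglycemia effects shown. Dropout is missing at random, and missing counts as non-response in 2c to 2e. Covariate adjustment and multiple imputation are not modelled.

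| Weight benefit | Hypoglycemia, IDegAsp vs iGlarLixi | 2b, 2d, 2e all rejected | Gain in points: 2a / 2c / 2b |
|---|---|---|---|
| 2 kg | 50% vs 30% | 98.5% | 10.8 / 10.9 / 0.0 |
| 1 kg | 40% vs 40% | 37.2% | 3.3 / 4.6 / 0.1 |
| 0.5 kg | 30% vs 40% | 4.0% | 0.2 / 0.4 / 0.2 |

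**8. Cost at a zero HbA1c difference** (same assumptions, counting claims that favour iGlarLixi). In one direction the limit for 2a is 0.025/2 = 1.25% now and 0.05/2 = 2.5% with the return. Simulated false 2a claims rose from 1.2% to 2.5% (2 kg, 50% vs 30%) and from 1.2% to 1.6% (1 kg, 40% vs 40%).

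**The case against.** Ending a chain at its last endpoint is a legitimate and simpler choice, and the two documents and the interval rules are consistent with it. That stands: nothing here has to be corrected.

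A reader might infer that recycling is free because the 0.05 limit holds. The working does not support this. In the four configurations listed, the error bound doubles. One of them, {2a, 2c}, is what holds if HbA1c truly does not differ and the drugs differ in weight and the composites. Zero is the only HbA1c difference the documents assume. The current rule is stricter in exactly that case, and a sponsor may prefer it.

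The size of the gain rests on assumed weight and hypoglycemia effects and a simplified analysis, so it cannot show that the change matters in this trial. That stands too.

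The figures are not visible, so a return arrow cannot be excluded. The written levels and the fixed 97.5% intervals point against one.

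Timing is the most serious practical objection. The first participant was randomized on 18 July 2022 and the SAP is dated 14 November 2023, about 16 months later. The trial is open-label. Protocol 6.4 offers a safeguard: "To compensate for the lack of blinding, the Investigator and the Sponsor will not have access to the data of the primary efficacy parameters". It covers HbA1c, not the weight and hypoglycemia data that help open the new route. It is followed by an allowance that "the study team may review the data for the primary efficacy parameter in descriptive statistics with the name of the IMP treatment masked". A late change that can only add superiority claims needs clean documentation.

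**Conclusion.** The point holds as an optional improvement of low severity. The rules are valid and consistent. As written they leave 0.025 unused in four of 31 null configurations and cap 2a, 2b and 2c at 0.025. A return from 2e dominates the current rule in rejections and stays within the stated 0.05.

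At a true HbA1c difference of 0.20% the gain for 2a is roughly 0 to 11 points, near the top only with a large weight benefit. The price is a higher chance of a false claim in the four configurations: for 2a at zero difference, about 1.2% rising to between 1.6% and 2.5%. Gains and simulated costs depend on effects the documents do not state; the 0.05 bound and the finding that no rejection is lost do not.

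The documents do not support reading this as a failure of error control or as a general loss of power. Outside the narrow patterns described, both rules give the same decisions.

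**What to change.** If the sponsor wants the gain, add edges from 2e to 2a and from 2e to 2b (weight 1/2 each) and state in SAP 3.5 and Protocol 9.3.4:

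- If 2b, 2d and 2e are rejected and 2a is not, 2a is retested at 2-sided 0.05 and, if rejected, 2c is tested at 0.05.
- If 2a is rejected but 2c is not, and 2b, 2d and 2e are rejected, 2c is retested at 0.05.
- If 2a, 2c, 2d and 2e are rejected and 2b is not, 2b is retested at 0.05.

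Match both figures to this text. If the figures already carry a return arrow, correct the text to them. Report the intervals for 2a and 2b in SAP 3.3.1.2 and 3.3.1.3 at the level actually used, as the SAP already does for 2c to 2e.

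The cost is text edits in both documents, interval levels for 2a and 2b that depend on the results, and the credibility of a late change. It must be documented before database lock and before any by-arm review, including review with treatment names masked. If such a review has already taken place, leave the rule as it is.

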3.6 SAFETY ANALYSES

All safety analyses will be performed on the safety population as defined in [Section 2](#), unless otherwise specified, using the following common rules:

- The analysis of the safety variables will be essentially descriptive, and no testing is planned.
- Safety data in participants who do not belong to the safety population (eg, exposed but not randomized) will be provided.

3.6.1 Extent of exposure

The extent of IMP exposure will be assessed by the duration of IMP exposure and compliance and summarized within the safety population.

Duration of IMP exposure

Duration of IMP exposure is defined as: (Date of the last open-label IMP injection – Date of the first open-label IMP injection) + 1 day, regardless of unplanned intermittent discontinuations. If the date of the last dose of IMP is missing, the duration of IMP will be left as missing. Duration of IMP exposure will be summarized quantitatively and categorically: 1 to 14, 15 to 28, 29 to 56, 57 to 84, 85 to 126, 127 to 160, 161 to 168, and > 168 days.

Additionally, the cumulative duration of treatment exposure (expressed in participant-years and defined as the sum of the duration of treatment exposure for all participants divided by 365.25) will be provided.

In both treatment groups, final insulin dose at the end of the open-label randomized treatment period will be summarized quantitatively and categorically: 1 to 10, >10 to 20, >20 to 30, >30 to 40, and >40 U. For iGlarLixi group, the final lixisenatide dose at the end of the open-label randomized treatment period will be summarized quantitatively and categorically: 1 to 10, >10 to 15, >15 to 20, and >20 µg.

Treatment compliance

Overall treatment compliance is defined as the actual number of days with IMP injection compared to the planned number of days with IMP injection during the open-label treatment period, up to treatment discontinuation. It will be calculated according to the following formula:

Compliance rate (%) = total number of days with IMP injection / planned number of days with IMP injection * 100.

No imputation will be made for participants with missing or incomplete data.

Treatment compliance will be summarized quantitatively and categorically: <60%, ≥60% to <80%, ≥80% to ≤100%, and >100%.

3.6.2 Adverse events

General common rules for adverse events

All adverse events (AEs) will be coded to a lower-level term (LLT), preferred term (PT), high-level term (HLT), high-level group term (HLGT), and associated primary system organ class (SOC) using the Medical Dictionary for Regulatory Activities (MedDRA) version currently in effect at Sanofi at the time of database lock.

The AEs will be analyzed in the following 3 categories:

- Pre-treatment AEs: AEs that developed, worsened or became serious during the pre-treatment period.

- Treatment-emergent adverse events (TEAE)s: AEs that developed, worsened or became serious during the treatment-emergent period regardless of initiation of rescue medication, ie, from the first injection of open-label IMP to the last injection of open-label IMP + 3 days (1 day for hypoglycemia).
- Post-treatment AEs: AEs that developed, worsened or became serious during the post-treatment period, ie, 4 days (2 days for hypoglycemia) after last injection of open-label IMP to end of study.

Similarly, the deaths will be analyzed in the pre-treatment, treatment-emergent and post-treatment periods.

The primary AE analyses will be on TEAEs. Pre-treatment and post-treatment AEs will be described separately.

An AE with incomplete or missing date/time of onset (occurrence, worsening, or becoming serious) will be classified as a TEAE unless there is definitive information to determine it is a pre-treatment or a post-treatment AE. For the analysis of time to event, incomplete date of onset will be imputed to the earliest possible; after imputation, if the imputed date is earlier than the date of the first injection of IMP, it will be overwritten by date of the first injection of IMP.

If the assessment of the relationship to IMP is missing for an AE, this AE will be assumed as related to IMP. Missing intensity will be left as missing.

Multiple occurrences of the same event in the same participant will be counted only once in the tables within a treatment phase.

The AE tables will be sorted as indicated in [Table 4](#).

Table 4 - Sorting of AE tables

AE presentation	Sorting rules
SOC, HLGt, HLT and PT	By the internationally agreed SOC order and by alphabetic order of HLGts, HLTs and PTs.
SOC and PT	By the internationally agreed SOC order and decreasing frequency of PTs ^{a,b}
PT	By decreasing frequency of PTs ^a

^a Sorting will be based on the iGlarLixi intervention group.

^b The table of all TEAEs presented by primary SOC and PT will define the presentation order for all other tables (eg, treatment-emergent SAE) presented by SOC and PT, unless otherwise specified.

Analysis of all adverse events

The overview of TEAE with the details below will be generated:

- Any TEAE
- Any treatment-emergent SAE
- Any TEAE leading to death
- Any TEAE leading to permanent treatment discontinuation

The AE summaries of **Table 5** will be generated with number (%) of participants experiencing at least one event.

Table 5 - Analyses of adverse events

Type of AE	MedDRA levels
All TEAE	Primary SOC, HLGT, HLT and PT
	Primary SOC and PT
	Primary and secondary SOC, HLGT, HLT and PT
Common TEAE ($\geq 1\%$ in any group)	Primary SOC and PT
TEAE related to IMP as per Investigator's judgment	Primary SOC and PT
TEAE by maximal intensity	Primary SOC and PT
Treatment emergent SAE	Primary SOC, HLGT, HLT and PT
	Primary SOC and PT
Treatment emergent SAE related to IMP as per Investigator's judgment	Primary SOC, HLGT, HLT and PT
TEAE leading to permanent treatment discontinuation	Primary SOC, HLGT, HLT and PT
	Primary SOC and PT
TEAE leading to death ^a	Primary SOC, HLGT, HLT and PT
	Primary SOC and PT
Pretreatment AE	Primary SOC and PT
Post-treatment AE	Primary SOC and PT
Post-treatment SAE	Primary SOC and PT

^a Death as an outcome of the AE as reported by the Investigator in the AE page

Among all TEAEs, Kaplan-Meier curves will be provided, when appropriate, for the time to first onset of the following PTs: nausea, vomiting and diarrhea as appropriate.

The frequency of TEAEs over time will be provided for nausea, vomiting and diarrhea as appropriate, using weekly time intervals up to 24 weeks, ie, [0-1] week, (1,2] weeks, (2,3] weeks, (3,4] weeks, etc. In each time interval, the numerator in the calculation of percentages will be the number of participants with at least 1 TEAE occurring in this time interval. Two types of analyses will be included: (1) only the first event will be counted for each participant and all recurrent events will not be included, and the denominator for the calculation of percentages will be the number of participants at risk at the beginning of the time interval who did not experience a first event in the preceding intervals; graphical presentations will also be provided for the percentages of participants with nausea, vomiting and diarrhea as appropriate by week; and (2) the recurrent events in subsequent intervals will be counted once for each participant in the numerator of the corresponding interval, and the denominator for the calculation of percentages will be the number of participants at risk at the beginning of the time interval.

Analysis of deaths

In addition to the analyses of deaths included in [Table 4](#) the number (%) of participants in the following categories will be provided:

- Deaths during the treatment-emergent and post-treatment periods
- Deaths in non-randomized participants or randomized but not treated participants

Analysis of adverse events of special interest (AESIs)

Adverse events of special interest (AESIs) will be selected for analyses as indicated in [Table 6](#). Number (%) of participants experiencing at least one event will be provided for each event of interest, by primary SOC and PT if applicable. Tables will be sorted as indicated in [Table 4](#).

Table 6 - Selections for AESIs

AESIs	Selection

• Pregnancy of a female participant entered in a study as well as pregnancy occurring in a female partner of a male participant entered in a study with IMP/NIMP
- Pregnancy occurring in a female participant entered in the clinical trial or in a female partner of a male participant entered in the clinical trial. It will be qualified as an SAE only if it fulfills one of the seriousness criteria.- In the event of pregnancy in a female participant, IMP should be discontinued.- Follow-up of the pregnancy in a female participant or in a female partner of a male participant is mandatory until the outcome has been.• Symptomatic overdose (serious or nonserious) with IMP/NIMP
- An overdose (accidental or intentional) with the IMP/NIMP is an event suspected by the Investigator or spontaneously notified by the participant (not based on systematic pills count).• Increase in alanine transaminase (ALT) more than 3 times the ULN	e-CRF specific tick box on the AE page

